1.2 Study Aims/Objectives

Primary Objective:

1. To assess the effects of 12 weeks of Entresto on the functional clinical parameters maximal walking duration, pain free walking duration and 6 minute walk test of patients with PAD.

Secondary Objective:

1. To assess if changes in functional clinical parameters are related to improvements in microvascular and mitochondrial function and to assess the effects of increasing NP activity on arterial elasticity.
2. To assess the time required for functional improvements (6 minute walk test) to return to baseline

values following 12 weeks of Entresto.

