2.1 Study Design

This is a double blind, randomized, controlled clinical trial with a goal of enrolling 30 subjects. Individuals who meet the eligibility criteria will be admitted into the study and will be randomly assigned to 12 weeks of Entresto or the placebo group. A variable block randomization design will be used to ensure a balance in sample size between the two groups²⁸. Each patient will be given a series of life style and health questionnaires, ankle brachial index will be measured and they will perform a graded exercise test to determine, pain free and maximal walking duration. In addition they will also perform the 6 minute walking test. They will also have a fMRI and MRS at pre and post 12 weeks of the clinical trial.

Following the 12 weeks of the treatment period, patients will be evaluated at weeks 4 and 8 to assess if any changes occurred in PFWD MWD and the 6 minute walking test, life style and health questionnaires and the presence or absence of adverse events following withdrawal of Entresto or placebo.

3 Outcome Measures

3.1 Ankle brachial index (ABI), exercise testing, questionnaires, anthropometric measurements and blood pressure monitoring

Patients will have their ABI determined following standard procedures described by the American Heart Association³⁴. If the patient's ABI meets the inclusion criteria, then an exercise testing procedure to determine, PFWD and MWDt will be performed. In addition, on that same day the Mini Mental State Examination (MMSE), the Walking Impairment Questionnaire (WIQ), the NIH toolbox assessment test for memory and cognitive function will perform, and Quality of Life Questionnaire (PAD-QOL)³⁵ will be given to each participant. Body height and weight will be measured using standard anthropometric procedures³⁶. Ambulatory blood pressure monitors using the Omron BP742N (©Omron Healthcare Inc. Lake Forest, IL) will be provided and each participant will measure and record their own arm blood pressure three times a day for the duration of the study immediately after waking up, at noon before lunch and in the night before going to bed.

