Participant will undergo a baseline symptom-limited treadmill test as described below. The treadmill test will be used to determine MWD and PFWD and will be repeated at follow-up. The graded exercise test (GXT) is initiated at 2.0 mph (3.2 km/h) at 0% grade, and every 2 minutes the grade is increased by 2%³⁸. The time at which the participant first starts feeling claudication symptoms is defined as the pain free walking duration and the time at which participants has to stop walking is designated as the maximal walking duration. During the GXT, participants will rate their claudication pain severity every 30 seconds, using the following claudication pain scale: 1 = no pain, 2 = initial onset of mild claudication pain, 3 = moderate pain, 4 = submaximal and 5 = maximal claudication pain (point at which the participant will request to stop). Recent evidence suggest that the 6 minute walk test is an accurate predictor of the response to treatment, mortality rate and mobility loss in patients with PAD³⁹. Therefore, we will also perform the 6 minute walk test because it offers the possibility of an inexpensive, accurate and valid tool to assess the effects of Entresto. The 6 minute walk test will be performed in a 20 meter corridor⁴⁰. Patients will be asked to walk as quickly as they can along the corridor for 6 minutes to cover as much distance as possible. They will be allowed to stop if they have to, but will be encouraged to continue again as soon as they are able. During the time that the participant stops walking the clock will continue to run. At the end of test the distance covered is measured.

[figure not shown]

Figure 2. T_1 weighed image of the lower leg showing the distinct location of the soleus and medial gastrocnemius muscles.

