- Arterial elasticity testing using applanation tonometry in the radial artery. Patients in the supine position will have electrodes placed in their chest to record an EKG, will have a blood pressure taken and arterial pulse wave will be recorded for 30 seconds in the radial artery.
- A graded exercise testing procedure to determine pain free and maximal walking duration will be performed. Participant's blood pressure and EKG will be measured before, during and for 6 minutes following the exercise test. Contraindications outlined by the American College of Sports Medicine to perform and to stop an exercise test will be followed.
- The 6 minute walk test will be performed in a 20 meter corridor. Patients will be asked to walk as quickly as they can along the corridor for 6 minutes to cover as much distance as possible. They will be allowed to stop if they have to, but will be encouraged to continue again as soon as they are able. During the time that the participant stops walking the clock will continue to run. At the end of test the distance covered is measured.
- A Walking Impairment Questionnaire (WIQ), a 36-item short-form health survey (SF-36), and Quality of Life Questionnaire (PAD-QOL) will be given to each participant.
- Body height and weight will be measured using standard anthropometric procedures.
- Total body lean and fat mass will be determined using bioelectrical impedance from Valhalla Scientific body comp scale®.

Visit 2 (Baseline 2/Randomization)

The second screening visit will take place within 48 hours of Visit 1. The following tests and procedures will be performed:

- Women of child bearing potential will have a urine pregnancy test to verify they are not pregnant.
- MRS and fMRI will be performed in a 7 Tesla/90 cm whole-body actively shielded human

scanner.

- IDS will randomize and dispense the treatment drug or placebo.
- The subject will be given instructions on how to take the drug and will be provided a diary to keep track of any adverse events they are experiencing.

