6.5 Follow-up Visits

Visits 8 (Follow-up, Week 6 after End of Treatment Visit)

Subjects will return 6 weeks after their treatment has ended to assess if any changes have occurred in pain free walking duration, maximal walking duration during the 6 minute walking test. Subjects will have a Walking Impairment Questionnaire (WIQ) and Quality of Life Questionnaire (PAD-QOL) administered. The presence or absence of adverse events following withdrawal of study drug will be assessed.

Schedule of Events

Schedule of Events								
	Visit 1 Screening	Visit 2 Baseline	Study Visits 3-7					Follow-up Visit 8
Time Point		Day 0	Week 2	Week 4	Week 8	Week 12	Week 12	Week 18
Time estimates	4 hours	4 hours	1 hour	1 hour	1 hour	4 hours	4 hours	45 min
Obtain Consent	x							
Ankle brachial Index	x					x		
Duplex ultrasound ¹	x							
Arterial elasticity	X					X		
Questionnaires	x					x		x
Memory test	X							
Height, weight, lean and fat mass	X					X		
Treadmill test	x					x		x
6 minute walk	x	x					x	x
MRI		x					x	
Blood draw for labs	X	x	x	x	x	x	x	
Urine test		x					x	
Blood pressure ²	x	x	x	x	x	x	x	x
Pregnancy test ³	x	x	X	X	X	X	X	X
Receive drug/placebo		x	x	x	x			
Review blood pressure records and diary			x	x	x	x		

1. Screening visit could be 5 hours long if duplex ultrasound is required, if not it will last 4 hours.
2. Visit should occur within 24 hours of last dose of drug.
3. Blood draw at screening and end of treatment visit 1 are following 10 hour fasting to assess serum: creatinine and K⁺, sodium, glucose, and serum insulin. Study visits at weeks 2, 4 and 6 are also fasting 10 hours prior to blood draw to assess: serum glucose, creatinine and potassium.
4. Duplex ultrasound will be perform only on those patients without a duplex ultrasound for the diagnosis of renal artery stenosis within the last year.
5. NIH toolbox for cognitive function.

6. The treadmill GXT test will be used to determine pain free walking distance, maximal walking distance.
7. Subjects will be instructed to measure and record their blood pressure at home, 3 times daily during the treatment period.
8. For women of childbearing potential.

7. Data Handling and Record Keeping

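### Secondary objective 2 asks how long the 6-minute-walk gain lasts, but the follow-up visits conflict, none can time a return, and the baseline walk is not named

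*Combined protocol and SAP*

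**What the plan says.** Section 1.2 sets the second secondary objective as "To assess the time required for functional improvements (6 minute walk test) to return to baseline". The 6-minute walk test (6MWT) is also in the primary objective, which ends "pain free walking duration and 6 minute walk test of patients with PAD".

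Three places describe what happens after treatment stops:

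- Section 2.1: "Following the 12 weeks of the treatment period, patients will be evaluated at weeks 4 and 8 to assess if any changes occurred".
- Section 6.5: "Subjects will return 6 weeks after their treatment has ended to assess if any changes have occurred". This is Visit 8, the only follow-up visit described.
- Schedule of Events: one follow-up column, Visit 8 at Week 18, with a 6MWT marked.

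Before treatment, the schedule marks a 6MWT at Visit 1 (labelled Screening) and again at Visit 2 (labelled Baseline, Day 0). Section 6.1 calls these visits Baseline 1 and Baseline 2. It lists the walk at Visit 1 ("The 6 minute walk test will be performed in a 20 meter corridor"), but its Visit 2 list has no 6MWT.

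Section 9.1 lists t-tests, chi-square tests, simple and multiple regression, and repeated-measures analysis of covariance. It gives no definition of return to baseline and no method for estimating when it happens.

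**The concern.** An objective about duration needs enough off-treatment measurements to locate the return in time. The plan gives two incompatible sets of measurements, and neither locates it well. With no definition of return, the result could be reported in several ways once the data are known: by patient or by group mean, among all patients or only improvers, at any threshold.

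The unnamed baseline walk reaches beyond this objective. The 6MWT is a primary measure, so choosing Visit 1, Visit 2 or their mean alters every 6MWT change score, and the covariate wherever baseline is adjusted for. That choice is at present open after the data are seen.

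**Working it through.** **1. Off-treatment 6MWT times.** Section 2.1 gives weeks 4 and 8 after treatment. Section 6.5 gives week 6. The schedule gives Week 18 = 12 + 6, which agrees with 6.5. The weeks in 2.1 cannot be on-treatment visits, because the sentence places them after the 12-week period and goes on to speak of withdrawal of study drug.

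**2. What each plan can observe for one patient.**

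| Plan | Return-time intervals that can be told apart | Number |
|---|---|---|
| 6.5 and schedule | 0–6 weeks; more than 6 weeks | 2 |
| 2.1 | 0–4; 4–8; more than 8 weeks | 3 |

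**3. Whether a group-level time could be recovered from one visit.** Only by assuming a shape. Suppose, as an illustration, that half the mean Week 12 gain remains at Week 18.

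- Straight-line decline: baseline is reached 2 × 6 = 12 weeks after treatment.
- Exponential decline through the same two points: the share of the gain left at 12 weeks is 0.5^(12/6) = 0.25, and baseline is never exactly reached.

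The same holds for the proportion of patients who have returned. With exponential return times of median m, the share back by week 6 is 1 − 0.5^(6/m): 88%, 65%, 50%, 41% and 29% for m = 2, 4, 6, 8 and 12 weeks. Reading a share p back as a median under a constant (uniform) return rate gives 3/p instead. For 0.875 that is 3.4 weeks rather than 2; for 0.293 it is 10.2 rather than 12. One visit cannot tell these shapes apart. Neither shape comes from the documents.

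**4. Precision of the one quantity that a single visit does give.** Section 9.2 plans 15 per group. That figure reproduces: with 278/240 = 1.158 SD and a two-sided 5% t-test, power is 0.839 at 14 per group and 0.865 at 15, so 15 is the smallest size reaching 0.85. It was derived for pain free walking distance, and the documents give no SD for the 6MWT.

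Assume all 15 Entresto patients improved and were followed. Fifteen is a maximum, since section 4.6 does not replace withdrawals. If 8 of 15 had returned by week 6, the exact (Clopper-Pearson) 95% limits are:

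- lower: Beta(0.025; 8, 8) = 0.266
- upper: Beta(0.975; 9, 7) = 0.787

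That is 53% with an interval of 27% to 79%.

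**5. Baseline walk.**

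| Source | Visit 1 | Visit 2 |
|---|---|---|
| Schedule | Screening; 6MWT marked | Baseline, Day 0; 6MWT marked |
| Section 6.1 | Baseline 1; 6MWT listed | Baseline 2; 6MWT not listed |

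The schedule's label points to Visit 2. The visit text has a walk only at Visit 1. No sentence settles it.

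**The case against.** The strongest reply is that this is the second secondary objective of a 30-patient trial, that the conflict may be an editing remnant, and that the repeated-measures analysis in 9.1 already compares groups over time. Part of that stands. The analysis could use the baseline, Week 12 and Week 18 means, so it would be wrong to infer that no return time could ever be estimated. The limit is absolute for individual patients. For the group, a time could be extrapolated under an assumed decline that the plan does not state and one visit cannot check.

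A reader might also infer that section 2.1 is simply the error, since 6.5 and the schedule agree. The documents do not support that firmly. The schedule conflicts with other text on a separate visit: it puts Visit 5 at Week 8, while section 6.2, section 11.2 and the schedule's own footnote say week 6. Section 6.5 also has plural wording in its headings ("Visits 8 (Follow-up, Week 6 after End of Treatment Visit"), which may be left over from a plan with more than one visit. Which version governs is open.

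A third tempting inference is that the loose baseline undermines the primary result. It does not. Both candidate walks precede treatment, and Visit 2 falls within 48 hours of Visit 1, so either choice leaves the randomised week-12 comparison unbiased. What is at stake is precision and freedom to choose.

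The Visit 8 phrase "maximal walking duration during the 6 minute walking test" looks like a dropped conjunction. The schedule marks both a treadmill test and a 6MWT there, so nothing rests on it.

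Finally, restoring weeks 4 and 8 would not fully rescue the objective. That is correct, and it is why reconciling the visits is not enough without restating what will be reported.

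**Conclusion.** The point holds. The plan gives two follow-up schedules without saying which governs. Under the one in 6.5 and the schedule, a patient's return can be placed only before or after 6 weeks; under 2.1 it falls into one of three coarse intervals. Neither supports an estimated time to return without an assumed shape of decline. Return is undefined, and no listed analysis addresses it. Separately, the baseline 6MWT is not fixed for a measure that is also in the primary objective.

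The interval counts follow directly from the visit times and need no assumption. The 27% to 79% interval is an illustration that assumes 15 improvers, all followed, and 8 returns. This should be corrected before the data are analysed. It does not invalidate the primary comparison.

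**What to change.** Make sections 2.1 and 6.5 and the Schedule of Events agree on the off-treatment visits.

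**If the single Week 18 visit stands**, restate objective 2 as how much of the 6MWT effect remains 6 weeks after treatment. Estimate it by the Entresto–placebo difference at Week 18, using ANCOVA adjusted for baseline 6MWT, with a 95% CI. Give the within-arm changes (Week 18 minus baseline, Week 18 minus Week 12) as description. Make no claim about time to return. The cost is wording only; the downside is a less ambitious objective.

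**If weeks 4 and 8 stand**, correct 6.5 and the schedule, and report the between-group 6MWT difference at each visit with 95% CIs. Any patient-level return needs a definition fixed in advance. One example is the first off-treatment 6MWT at or below the patient's own baseline, among those above baseline at Week 12. Treat it as interval-censored (0–4, 4–8, more than 8 weeks), keep it descriptive, and show it for both arms, because patients selected for having improved will drift back through regression to the mean even on placebo. The cost is one extra visit per patient: up to 30 visits at the schedule's 45 minutes, or 30 × 0.75 h = 22.5 hours, plus the burden on patients.

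**In either case**, name in advance one baseline 6MWT (Visit 1, Visit 2 or their mean) for all 6MWT analyses, including the primary objective. Make the Visit 2 text and the schedule agree on whether a walk is done there. Naming the baseline takes one sentence.

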1.3 Hypothesis

We hypothesize that the combined activation of both NPR- A and B will lead to enhanced vascular and mitochondrial function, improving oxygen delivery and utilization leading to substantial improvements in the functional clinical parameters of patients with PAD. We also hypothesize that the combined activation of NPR-A and B results in increased delivery, distribution, diffusion and utilization of oxygen by active skeletal muscle fibers, thus improving clinical functional limitations in patients with PAD.

2 Study Design

2.1 Study Design

This is a double blind, randomized, controlled clinical trial with a goal of enrolling 30 subjects. Individuals who meet the eligibility criteria will be admitted into the study and will be randomly assigned to 12 weeks of Entresto or the placebo group. A variable block randomization design will be used to ensure a balance in sample size between the two groups²⁸. Each patient will be given a series of life style and health questionnaires, ankle brachial index will be measured and they will perform a graded exercise test to determine, pain free and maximal walking duration. In addition they will also perform the 6 minute walking test. They will also have a fMRI and MRS at pre and post 12 weeks of the clinical trial.

Following the 12 weeks of the treatment period, patients will be evaluated at weeks 4 and 8 to assess if any changes occurred in PFWD MWD and the 6 minute walking test, life style and health questionnaires and the presence or absence of adverse events following withdrawal of Entresto or placebo.

3 Outcome Measures

3.1 Ankle brachial index (ABI), exercise testing, questionnaires, anthropometric measurements and blood pressure monitoring

Patients will have their ABI determined following standard procedures described by the American Heart Association³⁴. If the patient's ABI meets the inclusion criteria, then an exercise testing procedure to determine, PFWD and MWDt will be performed. In addition, on that same day the Mini Mental State Examination (MMSE), the Walking Impairment Questionnaire (WIQ), the NIH toolbox assessment test for memory and cognitive function will perform, and Quality of Life Questionnaire (PAD-QOL)³⁵ will be given to each participant. Body height and weight will be measured using standard anthropometric procedures³⁶. Ambulatory blood pressure monitors using the Omron BP742N (©Omron Healthcare Inc. Lake Forest, IL) will be provided and each participant will measure and record their own arm blood pressure three times a day for the duration of the study immediately after waking up, at noon before lunch and in the night before going to bed.

3.2 Laboratory Procedures

Participants will come following an 10 hour fast to provide a venous blood sample for measurements

of plasma Na^+ , K^+ , glucose, creatinine, NT-proBNP, BNP, serum insulin and also urinary cGMP and creatinine. Urine pregnancy testing will be performed at each visit on women of childbearing potential. Before the blood draw, trained personnel will measure BP three times and the average of those measurements will be recorded.

3.3 Diagnostic Procedure for PAD

Diagnosis of PAD is described in detail in inclusion criteria. Patients will be asked for symptoms suggestive of intermittent claudication (IC) and will also have their brachial and ankle systolic blood pressure measured at both arms and legs. Patients will lie supine and will rest quietly for 5 minutes and systolic blood pressure (SBP) will be measured once in each arm following standard procedures³⁷. Systolic blood pressure at the brachial artery and at the dorsalis pedis and posterior tibialis artery will be measured using an 8 MHz doppler vascular probe and the highest blood pressure at those sites will be recorded. A ratio of highest SBP measured at the ankle divided by the highest SBP measured at the brachial (ABI) < 0.90 will meet the diagnostic criteria for PAD. If there are symptoms of IC, but ABI is > 0.90 than patients will perform a walking test using the Gardner protocol and if highest systolic BP at the ankle decreases by > 25 mmHg that is also diagnostic of PAD.

3.4 Determination of maximal and pain free walking duration and the 6 minute walk test

Participant will undergo a baseline symptom-limited treadmill test as described below. The treadmill test will be used to determine MWD and PFWD and will be repeated at follow-up. The graded exercise test (GXT) is initiated at 2.0 mph (3.2 km/h) at 0% grade, and every 2 minutes the grade is increased by 2%³⁸. The time at which the participant first starts feeling claudication symptoms is defined as the pain free walking duration and the time at which participants has to stop walking is designated as the maximal walking duration. During the GXT, participants will rate their claudication pain severity every 30 seconds, using the following claudication pain scale: 1 = no pain, 2 = initial onset of mild claudication pain, 3 = moderate pain, 4 = submaximal and 5 = maximal claudication pain (point at which the participant will request to stop). Recent evidence suggest that the 6 minute walk test is an accurate predictor of the response to treatment, mortality rate and mobility loss in patients with PAD³⁹. Therefore, we will also perform the 6 minute walk test because it offers the possibility of an inexpensive, accurate and valid tool to assess the effects of Entresto. The 6 minute walk test will be performed in a 20 meter corridor⁴⁰. Patients will be asked to walk as quickly as they can along the corridor for 6 minutes to cover as much distance as possible. They will be allowed to stop if they have to, but will be encouraged to continue again as soon as they are able. During the time that the participant stops walking the clock will continue to run. At the end of test the distance covered is measured.

[figure not shown]

Figure 2. T_1 weighed image of the lower leg showing the distinct location of the soleus and medial gastrocnemius muscles.

3.6 Mitochondrial functional testing with magnetic resonance spectroscopy (MRS)

The bioenergetics of the medial gastrocnemius (MG) and soleus (Sol) muscle (Figure 2) will be assessed using MRS before, during and following a 24 seconds isometric maximal voluntary contraction (MVC). MRS will be performed in a 7 Tesla/90 cm whole-body actively shielded human scanner (Siemens AG, Erlangen, Germany). Optimal positioning of the muscle volume in the isocenter of the magnet will be determined using scout image scans with three orthogonal slices and multislice gradient echo images (matrix size = 108×128 , 14 slices, 7 mm slice thickness, field of view = $13 \times 16 \times 20$ cm, echo time (TE) = 5 ms, TR = 0.4 s)³⁷.

These scans will be used to identify the MG

and the Sol muscle (Figure 2) and positioned near the center of the ^{31}P coil for acquisitions of a time-resolved ^{31}P MR spectra. Acquisition of MRS will be performed using a pulse-acquire ^{31}P MRS sequence with a small ^{31}P surface coil (6 cm diameter) tuned to the resonance frequency of phosphorus at 7T (120.7 MHz). A nominal 90° square excitation pulse (pulse width of 300 ms) with TR of 1 s, an acquisition bandwidth of 5000 Hz and 2,048 data points will be used to acquire phosphorus data^{42,43}. MRS data will be quantified with jMRUI using the AMARES time domain fit routine⁴⁴. The following parameters will be acquired by MRS: PCr content and pH at rest and at the end of a 16 s isometric contraction, the rate constant of PCr recovery (KPCr) and maximal rate of oxidative phosphorylation (V_{max}).

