3.6.1 Advantage of high field MRS

Figure 3 shows the ^{31}P spectra acquired using the 7T at the Center for Magnetic Resonance Research of the University of Minnesota by [name] and his collaborators⁴⁵. Collecting ^{31}P -MRS data at 7T offers more than twice as much signal to noise ratio (SNR) per unit time thus reducing measurement time compared to 3T magnet⁴⁶. In addition, the increase in SNR allows the measurement of MRS parameters in muscles of interest and with high temporal resolution (1 s). This is important because the Sol, as a postural muscle, is predominantly a slow twitch muscle (slow fatigue, primary source of ATP is oxidative phosphorylation) and the gastrocnemius muscles, are more active during locomotion, is a 50% fast twitch muscle (fast fatigue and primary source of ATP is anaerobic glycolysis). The effects of PAD on each muscle may be different and the benefits from treatment will depend on the metabolic characteristics of each muscle. Therefore, measuring oxidative phosphorylation in each muscle separately will provide us with a more accurate assessment of the effects of Entresto on the bioenergetics of skeletal muscles in patients with PAD.

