3.7 Measurement of tissue perfusion and oxygenation using functional MRI (fMRI)

Validations studies using near infrared spectroscopy showed that changes in tissue oxygenation and blood volume can be assessed using differences in the MR signal intensities acquired using a dual echo gradient recall echo-echo planar (GRE-EPI) MRI procedure^{55,56}. This technique found differences in microvascular function between type 2 diabetic patients and healthy individuals⁴⁸.

3.8 fMRI data acquisition

[figure not shown]

Figure 4. GRE-EPI signal intensity time course before (blue), during (red) and following 16 seconds of maximal voluntary contraction (green) at a 7T magnet. a = post-contraction baseline, b = post-contraction peak. Change SI = b – a.

fMRI and MRS data will be acquired on the same magnet during a procedure that lasts about 90 minutes. MR signal intensities (SI) will be acquired using a custom made 6 cm diameter surface proton/phosphorus coil. The same anatomical site used for the MRS data will be used to acquire the fMRI. Muscle functional MRI (fMRI) data will be acquired using a GRE, echo-planar imaging sequence for 30 s before, during a 3 min cuff-occlusion, and for the following 210 s. The same procedure will be performed again after a 5 minute rest period using a spin echo (SE) sequence with similar acquisition parameters except with a TE = 21

ms. The functional images will be acquired using an acquired matrix = 128×128 , slice thickness = 10 mm, repetition time = 1000 ms (defining the time resolution of the measurements), and TE = 15 ms. In addition, MRS data will be acquired using a global signal using a free induction decay and adjusting the parameters to acquired preferentially from the MG muscle using a TR = 6 s Ernst angle = 77° and a T1 of PCr in muscle for $7T = 4$ s.

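### Separate soleus and gastrocnemius 31P-MRS results are promised, but neither described acquisition separates the muscles, and the plan does not say which one supplies the endpoints

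*Combined protocol and SAP*

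**What the plan says.** Section 3.6 sets out to assess the bioenergetics of both MG and soleus. Section 3.6.1 argues that PAD and treatment may act differently on the two muscles, and concludes that "measuring oxidative phosphorylation in each muscle separately will provide us with a more accurate assessment". It also relies on a time resolution of 1 s.

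Two 31P acquisitions are described.

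- **Section 3.6:** "Acquisition of MRS will be performed using a pulse-acquire ^{31}P MRS sequence with a small ^{31}P surface coil (6 cm diameter"), with "A nominal 90° square excitation pulse (pulse width of 300 ms) with TR of 1 s, an acquisition bandwidth of 5000 Hz". Both muscles are to be placed near the centre of the coil. The section then lists PCr content, pH, kPCr and Vmax as the MRS parameters.
- **Section 3.8 (fMRI data acquisition):** a further acquisition "using a global signal using a free induction decay and adjusting the parameters to acquired preferentially from the MG muscle", with "TR = 6 s Ernst angle = 77° and a T1 of PCr in muscle for $7T = 4$ s".

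No voxel, slice or gradient selection is stated for 31P in either place. Section 3.8.1 draws separate MG and soleus regions of interest, but only on the functional images. The visit lists in sections 6.1 and 6.4 give no MRS settings.

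**The concern.** Kinetics for a single muscle need a signal that comes from that muscle. A surface coil collects from all the tissue in its sensitive region, so as written both acquisitions return a mixture, and no soleus spectrum is described at all. A conclusion that Entresto acts differently on slow-twitch and fast-twitch muscle would then rest on MRS data that do not separate the two.

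In addition, the two acquisitions have very different saturation. PCr content scales with the recorded signal, and so does Vmax if it is calculated from PCr content. Unless the endpoint acquisition and the correction are fixed in advance, these values have no defined scale. The MRS measures are the mitochondrial half of secondary objective 1 (section 1.2), and muscle separation cannot be restored once unlocalised scans have been taken.

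**Working it through.** **Inputs.** From section 3.6: nominal flip angle 90°, TR 1 s. From section 3.8: flip angle 77°, TR 6 s, PCr T1 4 s. From section 3.6.2: 3 min of recovery. Muscle-specific recovery constants are not in the documents; those in step 5 are assumptions.

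**1. The plan's own figure.** Ernst angle = arccos(E), with E = exp(−TR/T1).

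- TR 6 s: E = exp(−6/4) = 0.223, giving 77.1°. The stated 77° is reproduced.
- TR 1 s: E = exp(−1/4) = 0.779, giving 38.8°, against the nominal 90°.

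**2. Steady-state signal per shot.** S = sin(a)(1 − E)/(1 − E cos a), as a fraction of full magnetisation.

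| Scheme | Calculation | S | S/√TR |
|---|---|---|---|
| 1 s, 90° | 1 × 0.221/1 | 0.221 | 0.221 |
| 6 s, 77° | 0.974 × 0.777/(1 − 0.223 × 0.225) | 0.797 | 0.325 |
| 1 s, 38.8° | 0.627 × 0.221/(1 − 0.779 × 0.779) | 0.353 | 0.353 |

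The ratio of the two described schemes is 0.797/0.221 = 3.60 per shot. It is 3.07 if T1 is 3 s and 4.03 if T1 is 5 s. To recover full magnetisation, PCr would be multiplied by 1/0.221 = 4.52 under 3.6 and by 1/0.797 = 1.25 under 3.8.

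**3. Dependence on the flip angle.** Section 3.6 calls its 90° nominal, and a surface coil need not deliver it throughout. At an actual 60° and TR 1 s, S = 0.866 × 0.221/(1 − 0.779 × 0.5) = 0.31. The 22% therefore belongs to the nominal angle and is not a fixed bias.

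**4. Effect on kPCr.** If recovery is A − B exp(−kt) and saturation multiplies the signal by a constant c, the recorded curve is cA − cB exp(−kt). The rate k is unchanged; only the amplitudes are scaled.

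**5. Effect of mixing.** Assume recovery constants of 60 s for MG and 30 s for soleus, and 50% depletion in both. Let w be the share of signal from MG:

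s(t) = w(1 − 0.5 exp(−t/60)) + (1 − w)(1 − 0.5 exp(−t/30)).

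A single exponential fitted to this curve, sampled every 1 s over 180 s, gives:

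- w = 0.5: 41.8 s
- w = 0.7: 48.2 s
- w = 0.9: 55.7 s

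Each value lies between the two muscles and equals neither. The plan neither sets nor measures w.

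**The case against.** Section 3.8 opens its MRS sentence with "In addition, MRS data will be acquired using a global signal". On that wording it describes a second acquisition, and two acquisitions in one session need not conflict. A reader might infer that the sections are incompatible; the documents do not support that. The natural reading is also that section 3.6, which lists the parameters, is the endpoint source, and only its TR matches the 1 s resolution in 3.6.1. This is a reasonable guess, but the text does not say so, and it gives the section 3.8 acquisition no purpose.

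A reader might also infer that kPCr and Vmax cannot be derived at all. That goes too far. Step 4 shows that constant saturation drops out of kPCr, and a blended or MG-weighted kPCr is obtainable. Within one scheme, a constant factor also applies equally to both arms and both scans.

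The 3.6-fold figure is per shot, and section 3.6 takes six shots for each one in 3.8. Per square root of time the ratio is 0.325/0.221 = 1.47, so 3.6 should not be read as a loss of precision.

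Two papers cited at the pulse-acquire description have titles naming localised 31P methods, which may hint at what was intended. The sequence actually written is still pulse-acquire. Moving the coil from one muscle to the other might give partial selectivity, but this is not described.

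Three further inferences should be left aside:

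- That the scheme would change between a patient's two scans. Both visits specify the same scanner, and nothing suggests a change.
- That TR 6 s samples the contraction too sparsely. Contraction is described in section 3.6.2, whereas the acquisition text of section 3.8 describes cuff occlusion.
- That a pulse width of 300 ms is a design flaw. It may be a reading error from the PDF.

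**Conclusion.** The concern holds in limited form. The plan promises per-muscle 31P-MRS results without describing an acquisition that separates the muscles. It does not identify which of two acquisitions supplies PCr content, pH, kPCr and Vmax, and it states no saturation correction. At nominal flip angles and the stated T1 of 4 s, signal per shot is about 22% against 80% of full magnetisation. PCr content, and Vmax if based on it, are therefore not interchangeable between the two. The blending figures depend on assumed recovery constants and show only the direction of the problem.

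The reach is confined to the MRS part of a secondary, mechanistic objective. That objective asks about mitochondrial function without naming a muscle, so an MG-weighted measure can still serve it.

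**What to change.** 1. Name one acquisition, with its TR and flip angle, as the source of all MRS endpoints, stated alike in sections 3.6 and 3.8. Use it for both scans of each patient. If the other is kept, state its purpose.
2. State that PCr is corrected for saturation using the T1 of 4 s, and which flip angle the correction assumes.
3. Define the MRS endpoints as a single MG-weighted signal and remove the separate-soleus and fibre-type claim for MRS. Alternatively, name a localised sequence that supports the claim.
4. If TR 1 s is kept for time resolution, consider its Ernst angle of about 39°. This gives 0.35 instead of 0.22 signal per shot, a gain of 0.353/0.221 = 1.59. It is an option; the other changes do not depend on it.
5. Reconcile the contraction duration, given as both 24 s and 16 s within section 3.6 and again within 3.6.2.

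The cost is protocol wording and, at most, a scanner setting, with no extra visits or patients. The real downside of the MG-weighted option is giving up the per-muscle MRS claim; a localised sequence would keep it but has to be specified before scanning.
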